The inclusion and exclusion criteria for the current study follows the evidence-based clinical practice guideline recommendations from the ESC and ISTH and identify a population of patients with VTE who have a 3-8% of VTE recurrence per year. We have estimated a 12-month VTE recurrence rate of 6% in our proposed study population, exactly within this range of clinical and research equipoise.

Study Objectives

Primary Safety Objective: To quantitatively assess the International Society on Thrombosis and Haemostasis (ISTH) major bleeding at 12 months.

Primary Efficacy Objective: To quantitatively assess the 12-month rate of symptomatic, recurrent VTE, defined as the composite of deep vein thrombosis and/or pulmonary embolism.

Secondary Safety Objective: To quantitatively assess the 12-month rate of ISTH clinically relevant non-major bleeding.

Secondary Efficacy Objective: To quantitatively assess the composite of death due to cardiovascular cause, nonfatal myocardial infarction, stroke or systemic embolism, critical limb ischemia, or coronary or peripheral ischemia requiring revascularization (major adverse cardiovascular events, including major adverse limb events) at 12 months.

Study Design

600-patient U.S.-based, single-center, randomized, double-blinded, placebo-controlled study of apixaban 2.5 mg orally twice daily for extended prevention of recurrence after provoked VTE in patients with at least one persistent provoking factor who have completed at least 3 months of standard therapeutic anticoagulation and who have a low risk of bleeding.

Study Duration

The study will be completed in 36 months: 2 months for start-up (including Human Research Committee/Institutional Review Board [IRB] approval and finalizing the Case Report Form), 32 months for patient enrollment, follow-up, and data collection, and 2 months for data analysis and writing up the results (**Table 1**).

Table 1. Study timeline.

Milestone	Duration (months)
Start-up	2
Patient enrollment	20
Completion of data collection	12
Data analysis and completion of study report	2
TOTAL	36

Study Population

Patients who are 18 years of age or older with provoked deep vein thrombosis and/or pulmonary embolism, have completed at least 3 months of therapeutic anticoagulation, have a low risk of bleeding, and have at least one persistent provoking risk factor.

Low risk of bleeding is defined by several of the exclusion criteria:

- have contraindications to antithrombotic or antiplatelet therapy

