- B. If the study is terminated or suspended, prompt notification will be provided to all parties of the study.
- C. Patient enrollment may be paused or terminated early if the DSMB determines that the potential benefits of continuing the trial are unlikely to outweigh the risks. For example, if the probability of achieving the target primary endpoints falls below a certain threshold, the trial will be stopped or paused for re-evaluation.

2. Safety Stopping Rules

The study will be terminated by the DSMB and principal investigator at any point if the following stopping criterion is met:

- a. An excess of morbidity or mortality is observed in patients receiving apixaban.
- b. When 3 of the subjects receiving apixaban experience an unprovoked intracranial hemorrhage, confirmed by independent adjudication and did not have a protocol violation such that he/she cannot be considered as representative of the intended patient population.
- c. When 3 of the subjects receiving apixaban experience an unprovoked major bleed (including fatal hemorrhagic events) and did not have a protocol violation such that he/she cannot be considered as representative of the intended patient population.

3. Stopping Rules for Futility

The study will be terminated by the DSMB and principal investigator if any of the following stopping criteria is met:

- a. Fewer than 36 events are observed in the placebo group at the time of the 300th patient interim statistical analysis
- b. Enrollment progress has been limited such that the study does not have a reasonable chance of randomizing 600 patients even after efforts to remediate recruitment

Protocol Violations

The study staff will rapidly and firmly address any protocol violations with the DSMB. If a protocol violation is detected or suspected, the investigator(s) will first be asked to provide a written explanation. After reviewing the available information, the study staff will categorize protocol violations as either major (eligibility or

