6.6 Interim Analysis

We will conduct a pre-specified interim analysis to assess the primary safety and efficacy outcomes after 50% of the planned enrollment population has completed 12-month follow-up. This planned interim analysis will inform the Data Safety Monitoring Board on whether the study should be stopped early due to efficacy, safety concerns, or futility or continue to enroll the full 600-patient cohort. The following three elements are used in considering the interim analysis:

6.7 Stopping for safety:

In the event that three distinct occurrences of unprovoked intracranial hemorrhages or major bleeding episodes are observed within the group of patients receiving apixaban, a thorough investigation will be conducted. This investigation will involve a review by an adjudication committee to confirm the authenticity of these incidents, ensuring that there have been no breaches of the study protocol that could have contributed to the adverse events. If the committee determines that these incidents are indeed linked to the apixaban treatment, specific measures will be implemented in response to these findings.

The decision to take action upon the confirmation of three such events is rooted in the clinical expertise of the researchers involved in the study. This threshold was established after extensive deliberation and consultation with the Mass General–Brigham Institutional Review Board (IRB).

The IRB is an independent body responsible for protecting the rights and welfare of human subjects involved in research, and their guidance plays a crucial role in maintaining the ethical standards of the study.

6.8 Stopping for futility:

The futility stopping rule is in place to prevent the unnecessary continuation of a clinical trial if there is a high likelihood that the primary efficacy outcome rate in the placebo arm falls below 6%. This threshold is considered clinically safe and is set to ensure that resources are not wasted on a trial that is unlikely to produce meaningful results. The problem is framed as a hypothesis testing scenario, where the null hypothesis states that the primary efficacy rate is greater than or equal to 0.06, and the alternative hypothesis suggests that it is less than 0.06.

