If the null hypothesis is rejected, it indicates that the actual event rates in the placebo arm are less than 6%. To reject the null hypothesis, fewer than 4 events must be observed. In this context, the trial's progress will be assessed during an interim statistical analysis when the 12-month follow-up is completed for the 300th patient. At this point, if there are fewer than 4 events observed in the placebo group, the decision to terminate the trial will be considered.

6.9 Stopping for efficacy (superiority):

The efficacy stopping rule is a guideline used to determine whether a clinical trial should be terminated early based on the observed results. This rule is applied in situations where the data collected from the trial's participants, in this case, 300 patients, clearly demonstrates that the treatment being studied has a significantly higher efficacy than the placebo. The objective is to avoid exposing more patients to an inferior treatment (placebo) and to expedite the process of bringing a highly effective treatment to the market.

In this specific scenario, the efficacy stopping rule is based on the unadjusted hazard ratio, which is a measure of the relative risk of an event occurring in the treatment group compared to the placebo group. A hazard ratio of less than 0.1 is considered as "overwhelmingly superior efficacy," indicating that the treatment group has a much lower risk of the event than the placebo group.

To determine whether the trial should be stopped, a hypothesis test is conducted. The null hypothesis (H_0) states that the hazard ratio is larger than or equal to 0.1, while the alternative hypothesis (H_1) states that the hazard ratio is smaller than 0.1. If the null hypothesis is rejected based on the data collected from the enrolled patients, it would be concluded that the treatment has overwhelmingly superior efficacy compared to the placebo. As a result, the trial would be terminated early, allowing for a more rapid progression towards making the effective treatment available to patients who could benefit from it.

References

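### The SAP's only futility rule checks the placebo event rate and ignores the treatment effect, and neither document gives a numerical criterion for lack of effect

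*Combined protocol and SAP*

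**What the plan says.** SAP 6.8 (Stopping for futility) gives its purpose as making sure that "resources are not wasted on a trial that is unlikely to produce meaningful results". It turns this into a one-sample test on the placebo arm, in which "the null hypothesis states that the primary efficacy rate is greater than or equal to 0.06" and the alternative is a lower rate. The boundary is stated directly: "To reject the null hypothesis, fewer than 4 events must be observed". The test is applied "when the 12-month follow-up is completed for the 300th patient", and the consequence is advisory: "if there are fewer than 4 events observed in the placebo group, the decision to terminate the trial will be considered". No apixaban count, hazard ratio or conditional power appears. The only SAP interim rule that compares the arms on efficacy is 6.9, which concerns a hazard ratio below 0.1.

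The protocol (final version, Stopping Criteria) has three relevant items:

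- **General rule 1.C** says that "if the probability of achieving the target primary endpoints falls below a certain threshold, the trial will be stopped or paused for re-evaluation". It gives no number.
- **Futility rule 3.a** uses fewer than 36 placebo events, so it too looks at placebo alone.
- **Futility rule 3.b** concerns enrolment.

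In its Interim Analysis section the protocol also asks the DSMB to look at the placebo event rate and at event rates in both arms. Its rationale section says that the eligibility criteria "identify a population of patients with VTE who have a 3-8% of VTE recurrence per year".

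**The concern.** Futility normally means that the trial is unlikely to show a difference if it continues, and that depends on both arms. A low placebo count does not show futility if apixaban has fewer events still. An adequate placebo count is no sign of promise if apixaban has as many events or more. A rule that reads one arm can therefore put interim results in the wrong order: it prompts a stopping discussion for some results that favour apixaban and stays silent for results that have almost no chance of success.

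Two things are at stake. If the rule is acted on, power is lost when the placebo rate lies in the lower part of the protocol's own 3-8% range. If it stays silent, the DSMB has no pre-specified prompt when apixaban is not working. This is separate from the conflict between 36 events (protocol) and 4 events (SAP). Settling on 4 would leave the problem in place.

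**Working it through.** **Inputs.** The look is at 300 patients with 12-month follow-up (SAP 6.6, 6.8). Allocation is 1:1 (SAP 3.1), so about 150 patients per arm. The design rates are 6% on placebo and a 75% reduction, that is 1.5% on apixaban (SAP 6.1). The final sample is 300 per arm, tested at two-sided 0.05. Assumptions added here: exactly 150 per arm at the look, no loss, no alpha adjustment, and the uncorrected two-proportion test as a stand-in for the log-rank test.

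**Step 1: reproduce the boundary.** With X the placebo count, X ~ Binomial(150, 0.06):

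- P(X ≤ 3) = Σ(k=0..3) C(150,k) 0.06^k 0.94^(150−k) = 0.0186
- P(X ≤ 4) = 0.0499

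Fewer than 4 is therefore the exact boundary at one-sided 0.025. The SAP states no alpha for this test, so 0.025 is inferred. With 140 to 160 placebo patients, P(X ≤ 3) runs from 2.9% to 1.2%.

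**Step 2: how often the rule fires.** Only the placebo rate enters P(X ≤ 3), so these figures are the same for any apixaban effect.

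| True placebo rate | P(rule met) |
|---|---|
| 6% | 1.9% |
| 5% | 5.5% |
| 4% | 14.6% |
| 3% | 33.8% |
| 2% | 64.7% |

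**Step 3: conditional power (CP) at particular results.** For interim counts t (apixaban) and c (placebo),

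CP = Σ over i, j of Bin(i; 150, 0.015) × Bin(j; 150, 0.06) × 1{z(t+i, c+j) > 1.96},

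with z(a, b) = [(b − a)/300] / √[2p̄(1 − p̄)/300] and p̄ = (a + b)/600.

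A hand check uses the expected second-half counts, 150 × 0.015 = 2.25 and 150 × 0.06 = 9:

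- From 0 vs 3 the expected final result is 2.25 vs 12. Then p̄ = 0.02375 and z = 0.0325/0.01243 = 2.61, above 1.96.
- From 12 vs 9 it is 14.25 vs 18. Then p̄ = 0.05375 and z = 0.0125/0.01841 = 0.68.
- From 12 vs 4 it is 14.25 vs 13, which favours placebo.

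Full enumeration gives:

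| Apixaban vs placebo | CP, design rates | SAP 6.8 trigger met? |
|---|---|---|
| 0 vs 3 | 82% (59% at 2% placebo, 75% reduction) | Yes |
| 3 vs 3 | 34% (1.6% at 2% placebo, 75% reduction) | Yes |
| 9 vs 9 | 11.7% | No |
| 8 vs 4 | 1.5% | No |
| 12 vs 9 | 1.1% | No |
| 12 vs 4 | 0.02% | No |

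**Step 4: power if the rule is acted on (true 75% reduction).** The loss is P(rule met) × P(final success given rule met).

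| Placebo rate | Power, no rule | Loss | Power, rule acted on |
|---|---|---|---|
| 6% | 85.9% | 1.9% × 45% ≈ 0.8 points | 85.1% |
| 4% | 69.1% | 14.6% × 37% ≈ 5.4 points | 63.7% |
| 3% | 54.7% | 33.8% × 31% ≈ 10.4 points | 44.2% |

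**Step 5: compare a rule that uses both arms.** The table gives the probability of meeting each rule when apixaban has no effect.

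| Placebo rate | SAP 6.8 | CP < 10% |
|---|---|---|
| 6% | 1.9% | 45% |
| 3% | 34% | 25% |
| 2% | 65% | 15% |

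At a 6% placebo rate a 20% cut-off meets the rule 59% of the time. With a true 75% reduction, the 10% cut-off costs at most about 0.015 point of power at 6%, 4% and 3%. The 20% cut-off costs about 0.15 point at 6%.

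**The case against.** The strongest defence is that SAP 6.8 says what it tests: whether the placebo rate has fallen short of the 6% on which the sample size rests. That is a legitimate question, because at 3% full power is only 55% even with the assumed effect. Termination is only considered, so the power losses in Step 4 arise only if the rule is acted on. The DSMB sees both arms, can recommend stopping at any time, and has clause 1.C. All of this stands. It narrows the point to the missing lack-of-effect criterion, because discretion and a clause without a number are not a pre-specified rule.

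A reader might also infer that the flagged trials are mostly likely to succeed. The figures do not support that. With a true 75% reduction, the average chance of final success among flagged trials is 45%, 37% and 31% at placebo rates of 6%, 4% and 3%. The 0 vs 3 result is the most favourable one that the rule flags, and its 82% assumes 6% in the remaining patients after 2% was observed.

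Timing limits the practical harm. With 300 patients enrolled by month 10, the look falls at about month 22, after the planned 20 months of enrolment. Under uniform accrual the second half would already average about 22 − 15 = 7 months of follow-up, so treating it as wholly unobserved overstates what remains.

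Finally, conditional power under the design rates responds weakly to a low event rate: 0 vs 0 still gives 55%. It cannot replace the event-rate check.

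**Conclusion.** The point holds in this form: SAP 6.8 is a placebo event-rate check carrying the futility label. It is the SAP's only futility rule, and neither document has a quantified criterion for lack of effect. At the design placebo rate, a trial of an ineffective drug passes it about 98% of the time (100% − 1.9%), and any trial with 4 or more placebo events passes whatever the apixaban count.

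It would go too far to say that the rule never stops an ineffective drug. It fires for an ineffective drug exactly as often as for an effective one, which is 34% of the time at a 3% placebo rate. The accurate statement is that it never fires because the drug is ineffective.

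The figures rest on 150 per arm at the look, complete follow-up, a chi-square stand-in for the log-rank test and no alpha adjustment. The independence from the apixaban effect needs none of the assumptions about the final test, since it follows from the rule's single input. The change should be made, but it is an improvement to an advisory rule and does not invalidate the final analysis.

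**What to change.** 1. In SAP 6.8, make the futility trigger a non-binding criterion that uses both arms. At the 300-patient look, the DSMB considers stopping for futility if conditional power for the final ITT log-rank test (two-sided 0.05) is below 10%, computed under the design assumptions (6% placebo rate, 75% reduction) for the remaining information.
2. Put the same figure in protocol Stopping Criteria 1.C in place of the unspecified threshold.
3. Keep the placebo count as a separately labelled event-rate alert. It should prompt DSMB review together with conditional power at the observed placebo rate, and should not be a stand-alone futility trigger.
4. Reconcile protocol rule 3.a (36 events) with the SAP (4 events) in the same edit.

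The cost is SAP wording, a short edit to the protocol's stopping criteria and one calculation by the DSMB statistician from event rates by arm that the DSMB already reviews. A non-binding futility rule needs no alpha adjustment. The power loss is under 0.1 point at a 10% cut-off. The cut-off is the sponsor's choice: 10% would not catch 9 vs 9 (11.7%), whereas 20% would, for about 0.15 point of power. Because the design-based figure is insensitive to a low event rate, item 3 is a necessary part of the change.

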Study Duration: 36 months; enrollment period of up to 20 months with 12-month follow-up.

Primary Safety and Efficacy Outcomes:

Primary Safety Outcome: International Society on Thrombosis and Haemostasis (ISTH) major bleeding at 12 months.

Primary Efficacy Outcome: Symptomatic, recurrent VTE, defined as the composite of deep vein thrombosis and/or pulmonary embolism at 12 months.

[figure not shown]
Secondary Safety Outcome: ISTH clinically relevant non-major bleeding at 12 months.

Secondary Efficacy Outcome: The composite of death due to cardiovascular cause, nonfatal myocardial infarction, stroke or systemic embolism, critical limb ischemia, or coronary or peripheral ischemia requiring revascularization (major adverse cardiovascular events, including major adverse limb events) at 12 months.

Follow-Up: Follow-up will consist of Electronic Health Record (EHR) review at 12-months from study enrollment.

Interim Analysis: An interim analysis for the primary safety and efficacy outcomes will be performed when 300 subjects have completed 12-month follow-up.

Study Flow Diagram

DVT, deep vein thrombosis; PE, pulmonary embolism; VTE, venous thromboembolism

Figure 1. Study flow-diagram for a single-center, randomized placebo-controlled trial of extended low-intensity apixaban for high-risk provoked VTE.

Study Subject Contact Calendar:

Date	Event	Study Drug
Enrollment (Month 0)	Subject will be consented by study physician and randomized through the Investigational Drug Service computer randomization program.	3 months of study drug (apixaban or placebo) will be given during this visit or sent to subject within 2 business days of the enrollment visit via mail or courier.
Month 3	Study nurse check-in	First 3 months drug containers and unused drug collected via mail and returned to pharmacy for proper disposal, 3 additional months' worth of medication will be given or sent to subject.
Month 6	Study nurse check-in	Drug containers and unused drug collected via mail and returned to pharmacy for proper disposal, 3 additional months' worth of medication will be given or sent to subject.
Month 9	Study nurse check-in	Drug containers and unused drug collected via mail returned to pharmacy for proper disposal, 3 additional months' worth of medication will be given or sent to subject.
Month 12	End-of-treatment visit	All remaining medications, drug containers, and 12-month drug diary will be collected.

Abbreviations and Definitions

Listed in alphabetical order

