 - b. Review of relevant laboratory data from within the past three months. If laboratory data for a complete blood count, basic chemistry panel, and coagulation (prothrombin time and activated partial thromboplastin time) are not available from the past three months, these will be drawn at the initial study visit and paid for by the study.
 - c. Serum (β -HCG) or urine pregnancy test (u-HCG) for women of child-bearing potential
7. If the potential study subject does not meet all the inclusion criteria or meets any of the exclusion criteria, the rationale for exclusion from the study will be recorded in the screening section of the electronic case report form (eCRF).

Assessment of Enrollment

After 10 months of study recruitment, an assessment of enrollment will be conducted. If 300 study subjects have not been recruited by 10 months, activation of second study site, Brigham and Women's Faulkner Hospital, will be considered by the Study Investigators. Activation of the Brigham and Women's Faulkner Hospital as a study site will require submission to and approval by the Partners Human Research Committee/IRB.

Treatment Description

Subjects will begin anticoagulation within 3 weeks of passing the screening procedure. Subjects who are 18 years of age or older with provoked DVT and/or PE, have completed at least 3 months of therapeutic anticoagulation, have a low risk of bleeding, and have at least one persistent provoking risk factor will be randomly assigned to receive apixaban 2.5 mg orally twice daily or oral placebo for extended secondary prevention of VTE for a duration of 12 months.

If during the study period the patient requires an invasive procedure or surgery that necessitates the discontinuation of anticoagulation (study drug), apixaban should be held as per the prescribing guidelines (**Appendix**, http://packageinserts.bms.com/pi/pi_eliquis.pdf). If appropriate based on the judgment of the responsible clinician, apixaban should be restarted when safe to do so postoperatively.

Patients and providers will be blinded as to the study group assignment.

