6.1 Power Calculation

Our power calculation accommodates efficacy outcomes. This is an implementation of the power calculation method described in Section 14.12 (page 807) of Rosner (2006). The equation of power calculation based on 1:1 randomization is expressed as below:

$$Power = \Phi \left(\frac{\sqrt{m}|\lambda - 1|}{\lambda + 1} - Z_{1-\frac{\alpha}{2}} \right),$$

where m is the expected total number of events over both groups, n is the total sample size, p_E and p_c are the probabilities of event in treatment group and placebo group over the maximum time of the study, λ is postulated hazard ratios for the treatment over placebo.

We postulated the following anticipated parameters for the power calculation: a) by the end of follow up, the event rate of the placebo arm is 6% and there is 75% reduction rate with active treatment (low-intensity apixaban), i.e., the event rate of the placebo arm is 1.5%; b) the postulated hazard ratios for the treatment over placebo by 1-year follow-up ranges from 0.2-0.24. These anticipated parameters are based on previous studies ^{3,4}. In Figure 1, we provide the power analysis given certain sample size. The power under the significance of 0.05 is given for the total sample with 1:1 randomization ranging from 500-700. To achieve sufficient sample sizes needed for reach the power of 80%, we conservatively choose 600 patients to ensure the enough power.

[figure not shown]

Figure 1. The power calculation given the postulated hazard ratios and with 1:1 randomization. The red curve indicates the power of 80%.

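### The SAP's interim efficacy rule requires rejecting a hazard ratio of 0.1 or more with about 11 events, so the stated early stop for superiority cannot operate

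*Combined protocol and SAP*

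**What the plan says.** SAP section 6.6 places one interim analysis "after 50% of the planned enrollment population has completed 12-month follow-up", that is, at 300 of 600 patients. It tells the Data Safety Monitoring Board (DSMB) whether the study should be "stopped early due to efficacy, safety concerns, or futility or continue to enroll the full 600-patient cohort".

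SAP section 6.9 gives the efficacy rule. It first sets a threshold: "A hazard ratio of less than 0.1 is considered as" overwhelming superiority. It then says how the decision is made: "To determine whether the trial should be stopped, a hypothesis test is conducted". The null "states that the hazard ratio is larger than or equal to 0.1", the alternative is a hazard ratio below 0.1, and the trial ends early if the null is rejected. No significance level, sidedness, test statistic or event count is given.

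SAP section 6.1 assumes that "the event rate of the placebo arm is 6% and there is 75% reduction rate with active treatment", with postulated hazard ratios of 0.2 to 0.24.

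On timing, the Protocol Summary has an "enrollment period of up to 20 months with 12-month follow-up". The protocol's Assessment of Enrollment section uses 300 patients at month 10 as its checkpoint: "If 300 study subjects have not been recruited by 10 months", a second site is considered.

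**The concern.** A superiority stop normally tests against no effect (hazard ratio 1) at a strict level. Here the null boundary is 0.1, well beyond the effect the trial is designed to find. If apixaban performs as planned, the null in section 6.9 is true. If apixaban does far better than planned, about 11 events are still too few to separate a hazard ratio of 0 from one of 0.1.

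Section 6.9 gives its purpose as sparing further patients from placebo once benefit is overwhelming. A rule that cannot fire does not do this. The SAP and protocol would leave the DSMB without a working efficacy boundary, and any efficacy stop would have to be improvised with no alpha plan behind it.

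There is also a scheduling problem. The look is meant to inform whether to go on enrolling, but on the plan's own timetable enrolment will already have closed.

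**Working it through.** **Inputs.** Placebo rate 6% and 75% reduction, so 1.5% on apixaban (SAP 6.1); 1:1 allocation (SAP 3.1); look at 300 completed patients, about 150 per arm (SAP 6.6); null hazard ratio ≥ 0.1 (SAP 6.9). Because section 6.9 states no level, one-sided 0.05 and 0.025 are both used.

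**The plan's own figures.** The documents give no figure for the efficacy rule. The sample size does reproduce: 6% against 1.5%, two-sided 0.05, gives 279 per group with power 0.8005, as the protocol states. The SAP 6.1 power formula with 300 × (0.06 + 0.015) = 22.5 events gives 0.828 at a hazard ratio of 0.24 and 0.885 at 0.20, consistent with the claimed 80%.

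**Expected events at the look.** 150 × 0.06 + 150 × 0.015 = 9 + 2.25 = 11.25.

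**Test of the section 6.9 null.** With 1:1 allocation and a true hazard ratio of 0.1, each event falls on apixaban with probability close to 0.1/1.1 = 1/11. Given D events with none on apixaban, the one-sided exact p-value is (10/11)^D.

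| Apixaban vs placebo events | p against HR = 0.1 |
|---|---|
| 0 vs 9 | (10/11)^9 = 0.424 |
| 0 vs 11 | (10/11)^11 = 0.350 |
| 0 vs 31 | (10/11)^31 = 0.052 |
| 0 vs 32 | (10/11)^32 = 0.047 |
| 0 vs 39 | (10/11)^39 = 0.024 |

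The smallest rejecting results at one-sided 0.05 are 0 vs 32 or 1 vs 50; at 0.025, 0 vs 39. Thirty-two events in 150 patients is 21.3%, which is 3.6 times the design rate and 1.9 times the 11.1% registry rate, the highest placebo rate used in the protocol's sample size section. The completed 600-patient trial expects only 22.5 events in both arms together.

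**Chance of crossing (exact test, one-sided 0.05, 150 per arm).**

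| Placebo rate | True HR | Probability |
|---|---|---|
| 6% | 0.25 | 3 × 10⁻¹¹ |
| 6% | 0 (every event prevented) | P(Bin(150, 0.06) ≥ 32) = 3 × 10⁻¹⁰ |
| 11.1% | 0.25 | 3 × 10⁻⁶ |
| 11.1% | 0 | 2 × 10⁻⁴ |

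**Other test statistics, none on apixaban, one-sided 0.05.** A score test needs 28 placebo events. A likelihood-ratio test nominally rejects at 15, but it is anti-conservative there (exact p at 0 vs 15 is 0.24), and its chance of firing under the design assumptions is about 0.4%.

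**Contrast with a test of no effect.** Against a hazard ratio of 1, 0 vs 11 gives a two-sided p of 2 × 0.5^11 = 0.00098, which crosses p<0.001. At 6% against 1.5% with 150 per arm, the exact chance of crossing is 4.9% at p<0.001 and 8.2% at 0.0031. If apixaban prevents every event, the chance at p<0.001 is 29%.

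**Timing.** The 300th patient is planned at month 10 and completes follow-up at 10 + 12 = month 22. Enrolment is planned to close at month 20.

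**The case against.** The strongest objection is that the result depends on a test that section 6.9 never names, and that the section can be read differently. It calls the rule a guideline and first states the 0.1 threshold without a test. Read as a cut-off on the estimated hazard ratio, the rule would fire about 17% of the time under the design assumptions. This reading does not help the plan. The next paragraph says explicitly that a test decides, and a bare cut-off would have no error control: 0 vs 4 events would meet it and would also escape the futility rule (fewer than 4 placebo events), with a two-sided p against no effect of only 2 × 0.5^4 = 0.125.

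Several other points stand in part:

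- A rule that cannot fire spends essentially no alpha, so the final test, its type I error and its power are not harmed.
- A repaired rule would cross only about 5% to 8% of the time at the planned rates, so the practical gain is modest unless the drug does better than planned.
- Setting a bar above the design effect is a legitimate choice in itself. The defect is that this bar cannot be reached.
- The protocol has the DSMB establish stopping rules and lets it recommend stopping at any time. The charter is not among the documents, so a working boundary there cannot be excluded. General discretion is not a superiority boundary, however, and the protocol's list of DSMB recommendations covers termination for safety or futility only.
- The timing conflict holds on the planned schedule. With uniform accrual over more than 24 months, enrolment would still be open at the look. Even at month 22 many patients would still be on treatment, so a stop could still matter to them.

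**Conclusion.** The concern holds. As written, the efficacy rule in SAP section 6.9 cannot be triggered by any plausible result at the planned look: it needs at least 32 placebo events with none on apixaban, where 9 placebo events are expected. The chance of crossing is about 3 × 10⁻¹¹ at the planned rates, and only 2 × 10⁻⁴ at an 11.1% placebo rate with a drug that prevents every event.

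These figures assume about 150 patients per arm, an exact conditional test and one-sided 0.05. A score or likelihood-ratio test still does not reject at the expected event count, even with every event on placebo. Counting all enrolled patients at about month 22 (assuming uniform accrual over 20 months) raises the expected total to about 18 events, still short of 32.

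The harm is a stopping rule that does not work, not an inflated type I error. It should be corrected because the SAP presents it as a patient protection, and because its other possible reading would stop the trial on weak data.

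**What to change.** Choose one of two options.

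1. **Keep an efficacy stop.** Replace the null in section 6.9 with a hazard ratio of 1, and state the test, sidedness, nominal level and analysis set. A Haybittle-Peto level of p<0.001 is simple. An O'Brien-Fleming boundary of about 0.003, with about 0.049 left for the final test, presumes that the look falls at half the information. The SAP must therefore say whether the look uses only the first 300 patients or everyone enrolled by then: about 18 of 22.5 events at month 22 would be well over half.
2. **Drop the efficacy stop.** Delete section 6.9 and remove efficacy from the reasons for stopping in SAP 6.6 and in the protocol's Interim Analysis and DSMB sections. State that the look is for safety and futility only, which matches the protocol's list of DSMB recommendations.

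In either case, remove the wording about continuing to enrol all 600 patients, or state that enrolment is expected to be complete by the look and say what a stop would then mean for patients still on treatment.

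The cost is wording in the SAP, the protocol and the DSMB charter, and at most a fall in the final significance level from 0.05 to about 0.049. The SAP is dated March 2025 and does not say whether the look has taken place. If it has, option 2 or a plain statement of what was actually done is the only credible course, since a boundary set after the look protects nothing.
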